11.1 Antitumor Effect – Solid Tumors

For the purposes of this study, participants should be re-evaluated for response every 8 weeks.

Response and progression will be evaluated in this study using the new international criteria proposed by the Response Evaluation Criteria in Solid Tumors (RECIST) guideline (version 1.1) [*Eur J Ca* 45:228-247, 2009]. Changes in the largest diameter (unidimensional measurement) of the tumor lesions and the shortest diameter in the case of malignant lymph nodes are used in the RECIST criteria.

11.1.1 Definitions

Evaluable for Target Disease response. Only those participants who have measurable disease present at baseline, have received at least one cycle of therapy, and have had their disease re-evaluated will be considered evaluable for target disease response. These participants will have their response classified according to the definitions stated below. (Note: Participants who exhibit objective disease progression prior to the end of cycle 1 will also be considered evaluable.)

Evaluable Non-Target Disease Response. Participants who have lesions present at baseline that are evaluable but do not meet the definitions of measurable disease, have received at least one cycle of therapy, and have had their disease re-evaluated will be considered evaluable for non-target disease. The response assessment is based on the presence, absence, or unequivocal progression of the lesions.

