5.7 Criteria for Taking a Participant Off Study

Participants will be removed from study when any of the following criteria apply:

- Lost to follow-up
- Withdrawal of consent for data submission
- Death

The reason for taking a participant off study, and the date the participant was removed, must be documented in the case report form (CRF). In addition, the study team will ensure Off Treatment/Off Study information is updated in OnCore in accordance with DF/HCC policy REGIST-101.

Participants that receive protocol therapy will not be replaced in this trial.

DOSING DELAYS/DOSE MODIFICATIONS

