13.2 Sample Size, Accrual Rate and Study Duration

We would consider ERK inhibition therapy effective in the treatment of uveal melanoma if a 25% response rate was observed. To assess this, we will conduct a two-stage design comparing a null rate of 5% against the alternative rate of 25%. Thirteen patients will be enrolled into the first stage of the trial and if one or fewer responses are observed the trial will be terminated for lack of efficacy. If two or more responses are seen, an additional 12 patients will be enrolled into the second stage of the trial. If a total of three or more of the 25 total patients

have a response the treatment would be considered promising. With this number of patients there is a 1 sided type-1 error of 8% (target 10%) and 87% power (target 85%). If the true response rate is 5% then the probability is 0.86 of stopping at the end of the first stage.

Uveal melanoma, similar to cutaneous melanoma, is a disease which is predominantly found in patients of Caucasian descent. Thus our study will not have many patients from racial categories other than White with a few patients who are Hispanic or Latino.

Accrual Targets				
Ethnic Category	Sex/Gender			
	Females		Males	Total
Hispanic or Latino	2	+	3	= 5
Not Hispanic or Latino	8	+	12	= 20
Ethnic Category: Total of all subjects	10	+	15	= 25
Racial Category				
American Indian or Alaskan Native		+		=
Asian		+		=
Black or African American		+		=
Native Hawaiian or other Pacific Islander		+		=
White	10	+	15	=
Racial Category: Total of all subjects	10	+	15	= 25

(A1 = A2) (B1 = B2) (C1 = C2)

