13.5 Analysis of Primary Endpoints

The primary endpoint for this study is overall response rate in uveal melanoma by standard solid

tumor response criteria. The proportion of patients with best response of CR or PR will be presented with a 90% confidence interval estimated using the method of Atkinson and Brown, which allows for the two stage design.

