13.6 Analysis of Secondary Endpoints

Secondary endpoints for this study include the rate of disease control, time to tumor progression, duration of response, safety of BVD-523, overall survival and correlative studies looking at drug effect and association of response with GNAQ and GNA11 mutation.

Disease control rate. The proportion of patients with best response of CR, PR, or SD lasting at least 24 weeks will be presented with a 90% exact binomial confidence interval. For a sample of size 25, the confidence interval will be no wider than 0.35.

Overall survival. Overall survival (OS) is the time interval between the start of treatment and death from any cause. OS will be censored at the date of the last follow-up visit for patients who become lost to follow-up.

Time to tumor progression. Time to tumor progression (TTP) is the time interval between the dates of the start of trial treatment and first documentation of progressive disease. In the absence of documented progressive disease, follow-up will be censored at date of last disease assessment.

Duration of response. Duration of response (DoR) is defined among patients with objective response (confirmed CR or PR as best overall response) as the interval between dates of first documentation of objective response and first documentation of progressive disease. In the absence of documented progressive disease, follow-up will be censored at date of last disease assessment.

The time-to-event endpoints will each be summarized using the method of Kaplan-Meier. Point estimates for each endpoint will be presented with 90% confidence intervals derived using log(-log(endpoint)) methodology.

Safety and Tolerability. All adverse events recorded during the trial will be summarized. The incidence of events that are new or worsening from the time of first dose of treatment will be summarized according to system organ class and/or preferred term, severity (based on CTCAE grade), type of adverse event, and relation to study treatment. Deaths reportable as SAEs and non-fatal serious adverse events will be listed by patient and tabulated by primary system organ class, and type of adverse event.

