13.7.2 Evaluation of the Primary Efficacy Endpoint

All participants included in the study must be assessed for response to treatment, even if there are major protocol treatment deviations or if they are ineligible. Each participant should be assigned one of the following categories: 1) complete response, 2) partial response, 3) stable disease, 4) progressive disease, 5) early death from malignant disease, 6) early death from toxicity, 7) early death because of other cause, or 9) unknown (not assessable, insufficient data). By arbitrary convention, category 9 usually designates the "unknown" status of any type of data in a clinical database.

PUBLICATION PLAN

The results should be made public within 24 months of reaching the end of the study. The end of the study is the time point at which the last data items are to be reported, or after the outcome data are sufficiently mature for analysis, as defined in the section on Sample Size, Accrual Rate and Study Duration. If a report is planned to be published in a peer-reviewed journal, then that initial release may be an abstract that meets the requirements of the International Committee of Medical Journal Editors. A full report of the outcomes should be made public no later than three (3) years after the end of the study.

REFERENCES

9. [name] RJ, Atkins MB. Molecular targeted therapy for patients with melanoma: the promise of MAPK pathway inhibition and beyond. *Expert Opin Investig Drugs.* 2010;19: 1205-1216.

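### No sentence names the denominator of the primary response rate (11.1.1 classifies evaluable patients only, 13.7.2 covers everyone), and 3.1.2 and 11.1.2 disagree on which nodes are measurable

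*Combined protocol and SAP*

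**What the plan says.** **Denominator.** Section 11.1.1 gives a target-lesion response classification to "Only those participants who have measurable disease present at baseline, have received at least one cycle of therapy, and have had their disease re-evaluated". A note adds patients with objective progression before the end of cycle 1. The companion definition for non-target disease covers patients whose lesions "do not meet the definitions of measurable disease, have received at least one cycle of therapy, and have had their disease re-evaluated", so it carries the same one-cycle and re-evaluation conditions.

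Section 13.7.2 is wider: "All participants included in the study must be assessed for response to treatment", even after major deviations or if ineligible. Its categories run beyond CR, PR, SD and PD to "5) early death from malignant disease, 6) early death from toxicity, 7) early death because of other cause, or 9) unknown".

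Section 13.5 states the primary analysis: "The proportion of patients with best response of CR or PR will be presented with a 90% confidence interval", using a method that allows for the two stages. It names no analysis set.

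Other sections bear on the question. The success rule in 13.2 begins "If a total of three or more of the 25 total patients". Section 5.7 says "Participants that receive protocol therapy will not be replaced in this trial". Section 4.1 cancels the registration of anyone who is never treated.

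**Nodes.** Eligibility criterion 3.1.2 applies one limit, 10 mm on spiral CT or MRI, both to the longest diameter of non-nodal lesions and to the short axis of nodes. It then refers to Section 11. There, 11.1.2 requires a short axis of at least 15 mm on CT for a node to be measurable, and lists nodes from 10 to under 15 mm as non-measurable.

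**The concern.** This is a single-arm trial whose primary result is one proportion with one interval. A patient who dies early without a new scan, or who stops for toxicity in cycle 1 without objective progression, is in neither 11.1.1 set but does receive a 13.7.2 category. Such patients are mostly non-responders, so leaving them out raises the reported rate. Two analysts following different sections could publish different primary results from the same data, and the choice could be made after the data are seen.

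The nodal mismatch works at the other end. Criterion 3.1.2 as worded can admit a patient who, under 11.1.2, has no measurable lesion and so no route to a partial response.

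**Working it through.** **1. The plan's own figures.** Inputs from 13.2: 13 patients in stage 1, stop at 1 or fewer responses; 12 more in stage 2; promising at 3 or more of 25; rates 5% and 25%.

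P(stop) = P(Bin(13, p) ≤ 1). After continuing, the trial fails only with exactly 2 responses in stage 1 and none in stage 2, so

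P(promising) = 1 − P(stop) − P(Bin(13, p) = 2) × (1 − p)^12.

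- p = 0.05: P(stop) = 0.51334 + 0.35123 = 0.8646. P(promising) = 1 − 0.86458 − 0.11092 × 0.54036 = 0.0755.
- p = 0.25: P(stop) = 0.02376 + 0.10295 = 0.1267. P(promising) = 1 − 0.12671 − 0.20590 × 0.03168 = 0.8668.

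These match the stated 0.86, 8% and 87%.

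**2. Who falls between the two rules.** The first scheduled re-scan is in Cycle 2, Days 22 to 28 (5.2.5), that is, days 50 to 56 from the start of treatment. A patient who dies unscanned before then fails the re-evaluation condition. A patient who stops during cycle 1 for toxicity fails the one-cycle condition, even if the end-of-treatment visit provides a scan.

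**3. Effect on the reported result.** The documents give no non-evaluable rate, so 2 or 4 non-evaluable patients is an assumption, as is their split between stages. Stagewise ordering is assumed as the implementation of the interval named in 13.5. With n1 and n2 the stage sizes, let

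G(s; p) = Σ over x from 2 to n1 of P(Bin(n1, p) = x) × P(Bin(n2, p) ≥ s − x).

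For s responses at full enrolment, the lower 90% limit solves G(s; p) = 0.05 and the upper solves 1 − G(s + 1; p) = 0.05. For a stage 1 stop with one response, the limits solve P(Bin(n1, p) ≥ 1) = 0.05 and P(Bin(n1, p) ≤ 1) = 0.05.

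| Responders | Patients (stage 1 / total) | Rate | 90% limits | Change in rate | Change in upper limit |
|---|---|---|---|---|---|
| 3 | 13 / 25, all treated | 12.0% | 4.2 to 32.8% | – | – |
| 3 | 12 / 23 | 13.0% | 4.6 to 35.1% | +1.0 | +2.3 |
| 3 | 13 / 21 | 14.3% | 4.6 to 34.9% | +2.3 | +2.1 |
| 3 | 11 / 21 | 14.3% | 5.0 to 37.8% | +2.3 | +5.0 |
| 5 | 13 / 25, all treated | 20.0% | 8.5 to 38.4% | – | – |
| 5 | 11 / 21 | 23.8% | 10.2 to 44.5% | +3.8 | +6.1 |
| 1 (stop) | 13, all treated | 7.7% | 0.4 to 31.6% | – | – |
| 1 (stop) | 11 | 9.1% | 0.5 to 36.4% | +1.4 | +4.8 |

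The intervals are about 29 to 36 points wide.

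**4. Effect on the decision.** The rule counts responders. An excluded non-responder adds nothing to that count, so removing one from the denominator changes neither the stage 1 decision nor the final one. If the 13 and 25 are treated patients and 5% and 25% are rates among them, the figures in step 1 stand. They would move if recruitment continued until 13 and 25 patients were evaluable. The null rate among evaluable patients would then be 0.05/0.9 with 10% non-evaluable and 0.05/0.8 with 20%, giving type I errors of 0.096 and 0.124 against the 10% target. The no-replacement rule in 5.7 tells against that reading.

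**5. Nodes.** Take a patient whose only lesions are nodes of 12 mm short axis on CT. Under 3.1.2 the disease is measurable and the patient qualifies. Under 11.1.2 it is non-measurable. The patient is then assessed with the second table in 11.1.4.4, whose outcomes are CR, non-CR/non-PD, not evaluated and PD. With no PR row, only a CR would count as a response. The documents give no count of such patients. Section 2.1 names the liver as the most common first metastatic site and 3.1.9 requires disease amenable to biopsy, so they are probably few.

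**The case against.** The strongest reply is that the passages fit together. Section 11.1.1 is a definition of who gets a lesion-based classification and does not call itself an analysis set. Section 13.7.2 is headed as the evaluation of the primary efficacy endpoint and provides categories for everyone 11.1.1 leaves unclassified. With 13.2, 5.7 and 4.1 also pointing to all treated patients, the intended denominator is fairly clear. This stands, and it is why a reader who infers an outright contradiction, or a faulty design, goes further than the documents allow. What it does not supply is the missing sentence: 13.7.2 asks for categories but never says that they enter the denominator as non-response.

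Missing re-evaluations should also be limited. Early objective progression is evaluable, 5.2.7 asks for end-of-treatment imaging when the last scan is more than 4 weeks old, and 11.1.4.4 asks for progression to be documented after discontinuation. That reduces the number affected, but end-of-treatment imaging does not waive the one-cycle condition.

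Two further inferences are tempting and not supported. One is that the disease control rate settles the denominator, since 13.6 says "For a sample of size 25, the confidence interval will be no wider than 0.35". That sentence concerns another endpoint and is conditional on 25 patients. The exact 90% maximum at 25 is 0.3535, so the figure holds only by rounding. The other is that the opening of Section 11 admits patients with non-measurable disease alone. Its wording may simply mean patients with both kinds of lesion.

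On nodes, the reference from 3.1.2 to Section 11 offers a route to resolution, but 3.1.2 still states its own, different number.

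**Conclusion.** The point holds as a minor one. The plan leaves the denominator of its primary estimate, and the handling of early death and unknown, to inference. An evaluable-only reading would overstate the response rate by about 1 to 4 points and raise the upper 90% limit by about 2 to 6. That rests on an assumed 2 to 4 non-evaluable patients, all non-responders, and on stagewise ordering. The shift is small against the width of the interval.

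A reader might infer that the sample size, error rates or stage rules are at fault. They are not: the stated figures reproduce, and the go/no-go rule, type I error and power are unaffected provided the 13 and 25 count treated patients.

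The nodal thresholds do disagree as written. The consequence is confined to patients who qualify only through nodes of 10 to under 15 mm. They are probably few, but their number cannot be derived from the documents.

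**What to change.** - In 13.5 and 13.7.2, state that the response rate and its two-stage interval use all participants who received at least one dose, and that every category other than confirmed CR or PR, including early death and unknown, counts as non-response.
- Keep the 11.1.1 evaluable set for a supportive analysis, labelled as such.
- Reconcile the nodal threshold in 3.1.2 with the measurability definition in 11.1.2.

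The cost is a few sentences. The reported rate may be slightly less favourable than under an evaluable-only reading. Sample size, stage rules and data collection do not change.

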11.1.2 Disease Parameters

Measurable disease. Measurable lesions are defined as those that can be accurately measured in at least one dimension (longest diameter to be recorded) as ≥ 20 mm by chest x-ray or ≥ 10 mm with CT scan, MRI, or calipers by clinical exam. All tumor measurements must be recorded in millimeters (or decimal fractions of centimeters).

Note: Tumor lesions that are situated in a previously irradiated area might or might not be considered measurable.

Malignant lymph nodes. To be considered pathologically enlarged and measurable, a lymph node must be ≥ 15 mm in short axis when assessed by CT scan (CT scan slice thickness recommended to be no greater than 5 mm). At baseline and in follow-up, only

the short axis will be measured and followed.

Non-measurable disease. All other lesions (or sites of disease), including small lesions (longest diameter <10 mm or pathological lymph nodes with ≥ 10 to <15 mm short axis), are considered non-measurable disease. Bone lesions, leptomeningeal disease, ascites, pleural/pericardial effusions, lymphangitis cutis/pulmonitis, inflammatory breast disease, abdominal masses (not followed by CT or MRI), and cystic lesions are all considered non-measurable.

Note: Cystic lesions that meet the criteria for radiographically defined simple cysts should not be considered as malignant lesions (neither measurable nor non-measurable) since they are, by definition, simple cysts.

‘Cystic lesions’ thought to represent cystic metastases can be considered as measurable lesions, if they meet the definition of measurability described above. However, if non-cystic lesions are present in the same participant, these are preferred for selection as target lesions.

Target lesions. All measurable lesions up to a maximum of 2 lesions per organ and 5 lesions in total, representative of all involved organs, should be identified as **target lesions** and recorded and measured at baseline. Target lesions should be selected on the basis of their size (lesions with the longest diameter), be representative of all involved organs, but in addition should be those that lend themselves to reproducible repeated measurements. It may be the case that, on occasion, the largest lesion does not lend itself to reproducible measurement in which circumstance the next largest lesion which can be measured reproducibly should be selected. A sum of the diameters (longest for non-nodal lesions, short axis for nodal lesions) for all target lesions will be calculated and reported as the baseline sum diameters. If lymph nodes are to be included in the sum, then only the short axis is added into the sum. The baseline sum diameters will be used as reference to further characterize any objective tumor regression in the measurable dimension of the disease.

Non-target lesions. All other lesions (or sites of disease) including any measurable lesions over and above the 5 target lesions should be identified as **non-target lesions** and should also be recorded at baseline. Measurements of these lesions are not required, but the presence, absence, or in rare cases unequivocal progression of each should be noted throughout follow up.

11.1.3 Methods for Evaluation of Disease

All measurements should be taken and recorded in metric notation using a ruler, calipers, or a digital measurement tool. All baseline evaluations should be performed as closely as possible to the beginning of treatment and never more than 4 weeks before the beginning of the treatment.

The same method of assessment and the same technique should be used to characterize

each identified and reported lesion at baseline and during follow-up. Imaging-based evaluation is preferred to evaluation by clinical examination unless the lesion(s) being followed cannot be imaged but are assessable by clinical exam.

Clinical lesions. Clinical lesions will only be considered measurable when they are superficial (*e.g.*, skin nodules and palpable lymph nodes) and ≥ 10 mm in diameter as assessed using calipers (*e.g.*, skin nodules). In the case of skin lesions, documentation by color photography, including a ruler to estimate the size of the lesion, is recommended.

Chest x-ray. Lesions on chest x-ray are acceptable as measurable lesions when they are clearly defined and surrounded by aerated lung; however, CT is preferable.

Conventional CT and MRI. This guideline has defined measurability of lesions on CT scan based on the assumption that CT thickness is 5mm or less. If CT scans have slice thickness greater than 5 mm, the minimum size of a measurable lesion should be twice the slice thickness. MRI is also acceptable in certain situations (*e.g.* for body scans).

Use of MRI remains a complex issue. MRI has excellent contrast, spatial, and temporal resolution; however, there are many image acquisition variables involved in MRI, which greatly impact image quality, lesion conspicuity, and measurement. Furthermore, the availability of MRI is variable globally. As with CT, if an MRI is performed, the technical specifications of the scanning sequences used should be optimized for the evaluation of the type and site of disease. Furthermore, as with CT, the modality used at follow-up should be the same as was used at baseline and the lesions should be measured/assessed on the same pulse sequence. It is beyond the scope of the RECIST guidelines to prescribe specific MRI pulse sequence parameters for all scanners, body parts, and diseases. Ideally, the same type of scanner should be used and the image acquisition protocol should be followed as closely as possible to prior scans. Body scans should be performed with breath-hold scanning techniques, if possible.

FDG-PET. While FDG-PET response assessments need additional study, it is sometimes reasonable to incorporate the use of FDG-PET scanning to complement CT scanning in assessment of progression (particularly possible 'new' disease). New lesions on the basis of FDG-PET imaging can be identified according to the following algorithm:

- (a) Negative FDG-PET at baseline, with a positive FDG-PET at follow-up is a sign of PD based on a new lesion.
- (b) No FDG-PET at baseline and a positive FDG-PET at follow-up: If the positive FDG-PET at follow-up corresponds to a new site of disease confirmed by CT, this is PD. If the positive FDG-PET at follow-up is not confirmed as a new site of disease on CT, additional follow-up CT scans are needed to determine if there is truly progression occurring at that site (if so, the date of PD will be the date of the initial abnormal FDG-PET scan). If the positive FDG-PET at follow-up corresponds to a pre-existing site of disease on CT that is not progressing on the basis of the anatomic images, this is not PD.
- (c) FDG-PET may be used to upgrade a response to a CR in a manner similar to a biopsy in cases where a residual radiographic abnormality is thought to represent

fibrosis or scarring. The use of FDG-PET in this circumstance should be prospectively described in the protocol and supported by disease-specific medical literature for the indication. However, it must be acknowledged that both approaches may lead to false positive CR due to limitations of FDG-PET and biopsy resolution/sensitivity.

Note: A ‘positive’ FDG-PET scan lesion means one which is FDG avid with an uptake greater than twice that of the surrounding tissue on the attenuation corrected image.

PET-CT. At present, the low dose or attenuation correction CT portion of a combined PET-CT is not always of optimal diagnostic CT quality for use with RECIST measurements. However, if the site can document that the CT performed as part of a PET-CT is of identical diagnostic quality to a diagnostic CT (with IV and oral contrast), then the CT portion of the PET-CT can be used for RECIST measurements and can be used interchangeably with conventional CT in accurately measuring cancer lesions over time. Note, however, that the PET portion of the CT introduces additional data which may bias an investigator if it is not routinely or serially performed.

Endoscopy, Laparoscopy. The utilization of these techniques for objective tumor evaluation is not advised. However, such techniques may be useful to confirm complete pathological response when biopsies are obtained or to determine relapse in trials where recurrence following complete response (CR) or surgical resection is an endpoint.

Cytology, Histology. These techniques can be used to differentiate between partial responses (PR) and complete responses (CR) in rare cases (*e.g.*, residual lesions in tumor types, such as germ cell tumors, where known residual benign tumors can remain).

The cytological confirmation of the neoplastic origin of any effusion that appears or worsens during treatment when the measurable tumor has met criteria for response or stable disease is mandatory to differentiate between response or stable disease (an effusion may be a side effect of the treatment) and progressive disease.

